### 7.1.5.3 Survival follow-up

All patients who had PD determined by investigator and confirmed by BIRC or withdrew consent from further study assessments will subsequently be followed for survival information every 3 months until death, lost to follow-up or withdrawal of consent for survival. The investigator or his designee will collect this survival information and any new anti-neoplastic therapies for all patients until the final survival analysis.

Follow-up can be done via a phone contact. Antineoplastic therapies will be captured on the 'Antineoplastic therapies since discontinuation of study treatment' eCRF page following the last dose of the study treatment.

### 7.1.5.4 Replacement policy

Patients lost to follow-up or withdrawing consent from the study without observed BIRC confirmed PD will be censored for the primary analysis and will not be replaced.

### **7.1.6 Withdrawal of consent**

Subjects may voluntarily withdraw consent to participate in the study for any reason at any time. Withdrawal of consent occurs only when a subject:

- Does not want to participate in the study anymore, and
- Does not allow further collection of personal data

In this situation, the investigator should make a reasonable effort (e.g. telephone, e-mail, letter) to understand the primary reason for the subject's decision to withdraw his/her consent and record this information.

Study treatment must be discontinued and no further assessments conducted, and the data that would have been collected at subsequent visits will be considered missing.

Further attempts to contact the subject are not allowed unless safety findings require communicating or follow-up.

All efforts should be made to complete the assessments prior to study withdrawal. A final evaluation at the time of the subject's study withdrawal should be made as detailed in the assessment table.

Novartis will continue to keep and use collected study information (including any data resulting from the analysis of a subject's samples until their time of withdrawal) according to applicable law.

For US and Japan: All biological samples not yet analyzed at the time of withdrawal may still be used for further testing/analysis in accordance with the terms of this protocol and of the informed consent form.

For EU and RoW: All biological samples not yet analyzed at the time of withdrawal will no longer be used, unless permitted by applicable law. They will be stored according to applicable legal requirements.

[figure not shown]
### **7.1.7 Lost to follow-up**

For patients whose status is unclear because they fail to appear for study visits without stating an intention to withdraw consent, the investigator should show "due diligence" by contacting the patient, family or family physician as agreed in the informed consent and by documenting in the source documents steps taken to contact the patient, e.g., dates of telephone calls, registered letters, etc. A patient should not be considered lost to follow-up until due diligence has been completed. Patients lost to follow-up should be recorded as such on the appropriate Disposition eCRF.

## **7.2 Assessment types**

### **7.2.1 Efficacy assessments**

Tumor response will be assessed locally and by BIRC according to the Novartis guideline version 3.1 ([Appendix 1](#)) based on RECIST 1.1 ([Eisenhauer et al 2009](#)). Patients should have at least one documented measurable lesion at study entry as per RECIST 1.1. The imaging

assessment collection plan is presented in [Table 7-2](#). Details of the central review process will be described in the independent review charter.

Imaging data will be centrally collected and checked for quality by an imaging vendor designated by Novartis. The results of the central BIRC evaluations will be used for primary analysis purposes. The local investigator's assessment will be used for treatment decision making.

**Table 7-2 Imaging collection plan**

Procedure	Screening/Baseline	During Treatment/Follow-Up
CT or MRI (chest, abdomen, pelvis) with i.v. contrast	Mandated	Mandated until PD determined by investigator and confirmed by BIRC, every 6 weeks
CT or MRI of other metastatic sites (e.g., neck, etc.), if applicable	Only if other metastatic sites are suspected	Mandated if patient has other metastatic sites at baseline (following the same schedule as CT/MRI of chest/abdomen/pelvis) or otherwise, only if clinically indicated
CT or MRI of brain with i.v. contrast	Mandated	Mandated if positive at baseline (following the same schedule as CT/MRI of chest/abdomen/pelvis), or otherwise, only if clinically indicated
Whole body bone scan [e.g., Tc-99 bone scan, whole body bone MRI, fluorodeoxyglucose positron emission tomography (FDG-PET) or sodium fluoride (NaF)-PET]	Mandated	If clinically indicated
Localized bone CT, MRI or X-ray	Only if clinically indicated (for any lesions identified on the whole body bone scan that are not visible on the CT/MRI of chest/abdomen/pelvis)	Mandated if positive at baseline (following the same schedule as CT/MRI of chest/abdomen/pelvis), or otherwise, only if clinically indicated
Color photographs with a metric ruler (only if skin lesions are present)	Only if other skin metastases are present	Mandated if patient has skin lesions at baseline (following the same schedule as CT/MRI of chest/abdomen/pelvis) or otherwise, only if clinically indicated

### 7.2.1.1 Baseline imaging assessment

Imaging assessments will be performed at screening/baseline Day -28 to Day -1 prior to Cycle 1 Day 1.

Any imaging assessments already completed during the regular work-up of the patient within 28 days prior to start of treatment, including before signing the main study ICF, can be considered as the baseline images for this study. Any imaging assessments obtained after first dose cannot be considered baseline images.

#### Imaging requirements at baseline

- Patients must have measurable disease as per RECIST 1.1 ([Appendix 1](#)). Measurable (“target”) lesions include lytic or mixed (lytic + blastic) bone lesions with an identifiable soft tissue component that meets the measurability criteria per RECIST 1.1 ([Appendix 1](#)).
- Patients with only non-measurable lesions are not eligible.

- If the measurable disease is restricted to a solitary lesion, its neoplastic nature should be confirmed by cytology/histology.
- Any potentially measurable lesion that has been previously treated with radiotherapy should be considered as a non-measurable (“non-target”) lesion. However, if a lesion previously treated with radiotherapy has clearly progressed since the radiotherapy, it can be considered as a measurable lesion.

All measurable lesions up to a maximum of 5 nodal and/or non-nodal lesions in total (and a maximum of 2 lesions per organ), representative of all involved organs, should be identified as target lesions and recorded and measured at baseline.

### **Tumor assessments required at baseline**

The following assessments will be performed:

- Computed Tomography (CT) with IV contrast or Magnetic Resonance Imaging (MRI) of chest, abdomen and pelvis.
  - The preferred radiologic technique is CT with intravenous (IV) contrast. If a patient is known to have a contraindication to CT contrast media or develops a contraindication during the trial, a non-contrast CT of the chest (MRI is not recommended due to respiratory artifacts) plus a contrast-enhanced MRI (if possible) of the abdomen and pelvis should be performed.
- A whole body bone scan according to institutional guidelines [e.g. Tc-99 bone scan, whole body bone MRI, Fluorodeoxyglucose positron emission tomography (FDG-PET) or sodium fluoride positron emission tomography (NaF PET)].
  - After screening, whole body bone scans is not required, unless clinically indicated. If indicated, the same methodology as at screening should be used.
- Localized CT, MRI or X-rays of any skeletal lesions identified on the screening whole body bone scan, which are not visible on the chest, pelvis and abdomen CT/MRI.
  - If skeletal lesions are documented at baseline, scans need to be continued following the same schedule as CT/MRI of chest, abdomen and pelvis. The same methodology as at screening should be used.
- Brain CT with IV contrast or MRI scan.
  - If brain lesions are documented at baseline, scans need to be continued following the same schedule as CT/MRI of chest, abdomen and pelvis. The same methodology as at screening should be used. Contrast enhanced brain MRI is preferred, however, if MRI contrast is contraindicated, then MRI without contrast or CT with/without contrast is acceptable.
- Color photographs, if skin lesions are present, using a digital camera in clear focus, including a scale/ruler, in such a way that the size of the lesion(s) can be determined from the photograph.
  - If skin lesions are documented at baseline, photographies need to be continued following the same schedule as CT/MRI of chest, abdomen and pelvis.
- CT or MRI of any other site of disease not captured by any of the above listed images (e.g., neck).

- If additional sites of disease are documented at baseline, scans need to be continued following the same schedule as CT/MRI of chest, abdomen and pelvis. The same methodology as at screening should be used.

Chest x-ray or ultrasound must not be used to measure tumor lesions.

#### **7.2.1.2 Subsequent imaging for response assessment**

Imaging assessments as described in [Table 7-2](#) should be performed at the timepoints specified using the same imaging modality used at baseline, irrespective of study treatment interruption or actual dosing (see [Table 7-1](#)). Imaging assessments for response evaluation will be performed every 6 weeks starting from Day 1 of cycle 1 (+/- 4 days window).

Additional imaging assessments may be performed at any time during the study at the investigator's discretion to support the efficacy evaluations for a patient, if necessary. Clinical suspicion of disease progression at any time requires a physical examination and imaging assessments to be performed promptly rather than waiting for the next scheduled imaging assessment.

Each lesion that is measured at baseline must be measured by the same method (either same imaging method or by photography, including a metric ruler) and when possible, the same local radiologist/physician throughout the study so that the comparison is consistent. If an off-schedule imaging assessment is performed because progression is suspected, subsequent imaging assessments should be performed in accordance with the original imaging schedule.

Combined PET/CT may be used only if the CT is of similar diagnostic quality as a CT performed without PET, including the utilization of oral and IV contrast media. At the discretion of the Investigators, FDG-PET scans may be performed to document PD per RECIST 1.1 ([Appendix 1](#)).

All study imaging (including any off-schedule imaging studies) performed to evaluate progression or response should be submitted to the designated imaging vendor for quality control and review by the BIRC, promptly after acquisition.

#### **7.2.1.3 Transmission of efficacy data to BIRC**

All radiological assessments will be read locally and should be submitted promptly after acquisition to the imaging vendor designated by Novartis. Rapid image transmission to the central imaging vendor will be accomplished by transferring the images acquired by the investigator electronically in a secured website (e.g.: via the internet). In all instances, the process at the imaging vendor will ensure that the central reviewers remain blinded to the results of the local assessment and the expedited nature of the review.

#### **7.2.1.4 Timepoints without locally determined progression**

All imaging timepoints without locally determined progression will be read on an ongoing non-expedited basis as detailed in the imaging manual to be provided by the designated imaging vendor and independent review charter. However expedited review may be required at the time of the interim analysis. Results of these readings will not be communicated to the sites.

### **7.2.1.5 Timepoints at which progression is determined locally**

All patients who have disease progression determined by the local investigator require an expedited tumor response review by the BIRC. If PD has been determined locally at a timepoint, the investigator must seek an expedited review and indicate this request to the imaging vendor on a designated form or by alternative means identified by the imaging vendor. The imaging vendor will ensure that the BIRC reviewers are blinded to BIRC reading requests.

Rapid image transmission to the central imaging vendor may be accomplished by uploading all digital images acquired by the Investigator to the secure website provided by the imaging vendor. The imaging will undergo expedited central review (within 5 business days from the time of the receipt of images at the imaging vendor) and the results of the central review will be communicated to the site. While the investigator is awaiting the results of the central review, it is preferable that the patient continue on study treatment. However, during this time, the investigator should do whatever is medically necessary for his/her patient.

If the central review determines disease progression, then the patient may discontinue study treatment and subsequent follow-up tumor assessments are no longer required. Treatment with INC280 may be continued beyond RECIST 1.1-defined PD determined by the investigator and confirmed by BIRC, if, in the judgment of the investigator, there is evidence of clinical benefit and the patient wishes to continue on the study treatment.

If the central review does not determine disease progression, the patient should continue receiving the study treatment unless there is a medical need (i.e., rapid progression or clinical deterioration) for an immediate change in therapy per the investigator's clinical judgment.

Patients will continue to have imaging performed as per protocol ([Table 7-1](#)) until the central review determines disease progression.

Note: If an investigator would like to discuss the central review results, there will be an independent physician at the imaging vendor who is not part of the central review pool for this study. This independent physician will be able to discuss the central review findings with the investigator. The central reviewers are completely excluded from such discussion. The contact at the imaging vendor can arrange such a discussion, as specified in the manual provided by the designated imaging vendor.

### **7.2.2 Safety and tolerability assessments**

Safety will be monitored using the following clinical and laboratory assessments: hematology, chemistry, coagulation parameters, urinalysis, 12-lead ECG, pregnancy test as well as collecting of the adverse events and concomitant medications at every visit. For details on AE collection and reporting, refer to [Section 8](#). Significant findings that were present prior to the signing of informed consent must be included in the relevant medical history/current medical conditions page on the patient's eCRF. Significant new findings that begin or worsen after informed consent must be recorded on the Adverse Event page of the patient's eCRF.

### 7.2.2.1 Physical examination

A complete physical examination must be performed at screening and later as clinically indicated and will include the examination of general appearance, skin, neck (including thyroid), eyes, ears, nose, throat, lungs, heart, abdomen, back, lymph nodes, extremities, vascular, and neurological assessments.

A targeted (short) physical exam will be performed as per schedule in [Table 7-1](#) and will include the examination of general appearance and vital signs (blood pressure and pulse).

Information about the physical examination must be present in source documentation at the study site. Significant findings that were present prior to the signing of informed consent must be included in the Medical History page on the patient's CRF. Significant new findings that begin or worsen after informed consent must be recorded on the Adverse Event page of the patient's CRF.

### 7.2.2.2 Vital signs

Vital signs include body temperature, blood pressure and pulse measurements and will be performed as per schedule in [Table 7-1](#). Blood pressure (systolic and diastolic) and pulse should be measured after the patient has been sitting for five minutes.

### 7.2.2.3 Height and weight

Height in centimeters (cm) and body weight (to the nearest 0.1 kilogram [kg] in indoor clothing, but without shoes) will be measured. Height will be measured at screening only (Refer to [Table 7-1](#)).

### 7.2.2.4 Performance status

Assessment of ECOG performance status ([Table 7-3](#)) will be performed as per the assessment schedule in [Table 7-1](#), even if study treatment is being interrupted. More frequent examinations may be performed at the investigator's discretion, if medically indicated.

**Table 7-3 ECOG performance status scale**

Score	Performance Status
0	Fully active, able to carry on all pre-disease performance without restriction
1	Restricted in physically strenuous activity but ambulatory and able to carry out work of a light or sedentary nature, e.g. light housework, office work
2	Ambulatory and capable of all self-care but unable to carry out any work activities. Up and about more than 50% of waking hours
3	Capable of only limited self-care, confined to bed or chair more than 50% of waking hours
4	Completely disabled. Cannot carry on any self-care. Totally confined to bed or chair
5	Dead

### 7.2.2.5 Laboratory evaluations

Novartis-designated central laboratories will be used for the analysis of scheduled hematology, biochemistry and other blood specimens collected as part of safety monitoring (as detailed in [Table 7-4](#)). The frequency of the assessments is indicated in [Table 7-1](#). Dipstick urinalysis

will be performed locally, except in the case of any significant findings, a urine sample will be sent to central laboratory for further microscopic analysis. Laboratory values obtained prior to treatment from central laboratory will be used to assess patient's eligibility. Only laboratory results from the Novartis-designated central Laboratory can be used to determine patient's eligibility for the study. The time windows granted for laboratory evaluations are identical to the corresponding visit time windows for each visit (refer to [Section 7.1](#)).

Local laboratory assessments may only be performed when an immediate clinical decision needs to be made. In those cases locally unscheduled testing may be performed. However samples should also be sent to the central lab. In such cases, local laboratories values should be recorded on the local laboratory eCRFs as unscheduled visits only if a severity grade differs from a severity grade reported by the central laboratory.

Each time local laboratory results are reported on the unscheduled local laboratory eCRF page, the study monitor will collect and submit promptly the local laboratory normal ranges and local laboratory certification.

Details on the collection, shipment of samples and reporting of results by the Novartis-designated central laboratory are provided to investigators in a separate [\[Laboratory Manual\]](#).

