Grade 4	Omit dose until resolved to ≤ grade 2 and then ↓ 1 dose level Mandatory: If toxicity recurs, discontinue patient from study drug treatment.
RENAL	
Serum creatinine	
Grade 1 (> ULN - 1.5 x ULN)	Maintain dose level
Grade 2 (> 1.5 - 3.0 x ULN)	Omit dose until resolved to ≤ grade 1 or baseline, then resume treatment at the same dose level.
Grade 3 (> 3.0 - 6.0 x ULN)	Omit dose until resolved to ≤ grade 1 or baseline, then resume treatment at ↓ 1 dose level.
Grade 4 (> 6.0 x ULN)	Mandatory: Permanently discontinue patient from study drug treatment
HEPATIC	
Isolated Total Bilirubin elevation*	
Grade 1 (> ULN - 1.5 x ULN)	Maintain dose level
Grade 2 (> 1.5 - 3.0 x ULN)	Omit dose until resolved to ≤ grade 1, then If resolved in ≤ 7 days, maintain dose level If resolved in > 7 days, ↓ 1 dose level
Grade 3 (> 3.0 - 10.0 x ULN)	Omit dose until resolved to ≤ grade 1, then If resolved in ≤ 7 days, ↓ 1 dose level If resolved in > 7 days, discontinue INC280 permanently
Grade 4 (> 10.0 x ULN)	Mandatory: Permanently discontinue patient from study drug treatment
Isolated AST or ALT elevation	
Grade 1 (> ULN - 3 x ULN)	Maintain dose level
Grade 2 (> 3.0 - 5.0 x ULN)	Maintain dose level
Grade 3 (> 5.0 - 20.0 x ULN)	Omit dose until resolved to ≤ grade 1 (or ≤ grade 2 if grade 2 elevation at baseline) then

Recommended dose modifications for INC280	
Worst toxicity CTCAE Grade a	
During a cycle of therapy
 
If resolved in <math>\leq</math> 7 days, then resume treatment at the same dose level If resolved in <math>></math> 7 days, resume treatment at <math>\downarrow</math> 1 dose level

Grade 4 ( $> 20.0 \times$ ULN)	
For patients with clinical benefit from INC280 upon investigator's judgement:
 
 
Omit dose until resolved to <math>\leq</math> grade 1 (or <math>\leq</math> grade 2 if grade 2 elevation at baseline), then resume treatment at <math>\downarrow</math> 1 dose level. Only 1 dose reduction is allowed; if this AE reoccurs at Grade 3 or above, discontinue INC280 permanently.
 
 
For all other patients:
 
 
Mandatory: Permanently discontinue patient from study drug treatment
 

Combined elevations of AST or ALT and Total Bilirubinb,d	

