#### 7.2.2.5.2 Clinical chemistry

Blood chemistry assessments of the parameters listed in [Table 7-4](#) will be tested as per the schedule of assessments ([Table 7-1](#)).

More frequent clinical chemistry testing may also be performed as medically necessary. Additional results from unscheduled clinical chemistry lab evaluations should be recorded on the appropriate Unscheduled Visit eCRF.

Note: Creatinine clearance should be calculated (e.g Cockcroft-Gault formula) at screening and need to be repeated on Cycle 1 Day 1 before first dose, unless screening assessment was performed within 7 days prior to the Cycle 1 Day 1 visit.

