- *Improved: Event with a non-missing end date and outcome “recovering/not resolving”. Event with a lower grade are expected to be reported*
- *Resolved: Event with a non-missing end date and outcome “recovered/ not resolved” or “resolved/resolved with sequelae”*

[Section 4.7.4](#) provides further details on the definition of first occurrence and duration.

Deaths

Separate summaries for on-treatment and all deaths will be produced by cohort, primary system organ class and preferred term.

All deaths will be listed, post treatment deaths will be flagged.

Laboratory data

For laboratory data assessments, data from all sources (central and local laboratories) will be combined. The summaries will include all laboratory assessments collected no later than 30 days after study drug discontinuation. All laboratory assessments will be listed and those collected later than 30 days after study drug discontinuation will be flagged in the listings.

Laboratory data will be classified (by Novartis Oncology Statistical Programming) into CTC grades according to the NCI CTCAE v4.03. For all reports, CTC grade is always obtained on the converted measurement in SI unit. Grade 5 will not be used. The CTC grade 0 will be assigned as below in different scenarios:

- For lab parameters defined by criteria based on normal range only, a severity grade of 0 will be assigned when the value is within normal limits.
- For lab parameters whose grade is defined by criteria based on normal range and absolute values (e.g. platelet count decrease). A severity grade of 0 will be assigned when the value is within normal limits.

- For lab parameters whose grade is defined by criteria based on normal range and the change from baseline value, with no other associated clinical criteria such as concomitant medication (e.g. creatinine increased) the following will be applied. For the baseline grading and for the grading of post-baseline lab values with missing baseline grading, the grade will be derived using the criteria based only on the normal range as per CTCAE v4.03. A severity grade of 0 will be assigned when the post-baseline value is \leq ULN (for hyper) or \geq LLN (for hypo).

Parameters for which a grading does not exist will be classified into low/normal/high group by means of laboratory normal ranges.

The following summaries will be produced by cohort for the hematology and biochemistry laboratory data (by laboratory parameter):

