- Shift tables using CTC grades to compare baseline to the worst post-baseline value for laboratory parameters with CTC grades
- Shift tables using low, normal, high (as well as low and high combined) classifications to compare baseline to the worst post-baseline value for laboratory parameters where CTC grades are not defined.
- New or worsened abnormalities for laboratory parameters based on CTC grade
- Trends of renal function parameters (creatinine, BUN) over time (baseline and selected on-treatment time-points, See [Table 4-6](#)) will be displayed via boxplots based on time windows and corresponding tables displaying the statistics used for the box plots by the selected time points.

The following lab parameters will be summarized by cohort:

- Hematology: absolute lymphocytes, absolute neutrophils, hemoglobin (anemia), WBC, platelet counts, absolute basophils, absolute eosinophils, absolute monocytes, hematocrit
- Biochemistry: alkaline phosphatase (ALP), SGPT (ALT), SGOT (AST), total bilirubin, amylase, potassium, sodium, creatinine, glucose (hypo only), phosphate, albumin, calcium, magnesium, creatinine, direct bilirubin, blood urea nitrogen (BUN), GGT, lipase.
- For bi-directional parameters, both hyper and hypo summaries will be presented.

The following laboratory parameters will be presented in listings and will not be summarized:

- Urinalysis: macroscopic panel (dipstick) (bilirubin, blood, glucose, WBC, pH, protein, specific gravity), Urinalysis Microscopic panel (RBC, WBC, casts).
- Coagulation: INR, pro-thrombin time (PT) or Quick Test

The following listings will be produced for the laboratory data for all laboratory parameters where CTC grades are defined:

- Listing of patients with laboratory abnormalities of CTC grade 3 or 4
- Listing of all laboratory data with values flagged to show the corresponding CTC grades and the classifications relative to the laboratory reference ranges.

Liver function parameters of interest are total bilirubin (TBIL), ALT, AST and alkaline phosphatase (ALP). The number (%) of patients with worst post-baseline values will be summarized by cohort in the following categories:

- ALT >3×ULN, >5×ULN, >8×ULN, >10×ULN, >20×ULN
- AST >3×ULN, >5×ULN, >8×ULN, >10×ULN, >20×ULN
- ALT or AST >3×ULN, >5×ULN, >8×ULN, >10×ULN, >20×ULN
- TBIL > 2×ULN, >3×ULN

Combined and concurrent values post-baseline

- ALT or AST > 3×ULN & TBIL > 2×ULN
- ALT or AST > 3×ULN & TBIL > 2×ULN & ALP \geq 2×ULN

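### Local liver results are entered only when their grade differs from the central grade, yet the bilirubin 2 × ULN cut-off and some transaminase cut-offs (not 3 × ULN) lie inside one grade

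*Protocol*

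**What the plan says.** **Data entry.** Protocol 7.2.2.5 limits local laboratory work to situations where an immediate clinical decision is needed. It adds "However samples should also be sent to the central lab", and then states that "local laboratories values should be recorded on the local laboratory eCRFs as unscheduled visits only if a severity grade differs from a severity grade" reported centrally. Protocol 7.2.2.5.2 gives a different instruction for chemistry: "Additional results from unscheduled clinical chemistry lab evaluations should be recorded on the appropriate Unscheduled Visit eCRF". It attaches no grade condition.

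**Grades.** Protocol Table 6-3 prints the bands. For total bilirubin: "Grade 2 (> 1.5 - 3.0 x ULN". For AST or ALT: "Grade 1 (> ULN - 3 x ULN" and "Grade 2 (> 3.0 - 5.0 x ULN", then grade 3 above 5 and up to 20 × ULN, and grade 4 beyond that.

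**Liver criteria.** Protocol 6.3.4.1 defines potential drug-induced liver injury (DILI). With normal baseline values it needs AST or ALT above 3 × ULN together with bilirubin above 2 × ULN. With an elevated baseline the transaminase limb is the lower of two limits: twice baseline (and above 3 × ULN), or 8 × ULN. The bilirubin limb is then above both twice baseline and 2 × ULN.

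**Analysis.** SAP 2.8.2 states that "data from all sources (central and local laboratories) will be combined". It tabulates worst post-baseline ALT and AST above 3, 5, 8, 10 and 20 × ULN, bilirubin above 2 and 3 × ULN, and combined rows such as "ALT or AST > 3×ULN & TBIL > 2×ULN". It also plots peak bilirubin against peak ALT/AST (eDISH). For the liver summaries, SAP 4.7.1 takes the worst value whichever laboratory produced it, even when different analytes come from different laboratories.

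**The concern.** The entry rule compares grades, while the liver criteria and tables compare multiples of ULN or of baseline. Where a cut-off lies inside a grade, two results can share a grade and still fall on opposite sides of it. The rule then leaves out the local result, even when it is the one above the cut-off.

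The loss runs in one direction. The analysis uses the maximum of the recorded values, so leaving out a local value can lower that maximum or leave it unchanged, never raise it. The combined criterion needs both limbs, so losing the bilirubin value alone can take a patient out of the combined rows. Local tests are drawn for urgent decisions, which is when values near these limits are most likely. Hepatotoxicity is an adverse event of special interest in both documents, so these tables will be read closely.

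**Working it through.** No stated figure is at issue. The check places each cut-off in the grade bands and then applies the entry rule.

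**Step 1. Fixed cut-offs** (bands from Table 6-3; cut-offs from Protocol 6.3.4.1 and SAP 2.8.2).

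| Cut-off (× ULN) | Grade at the cut-off | Grade just above | Can a straddling pair share a grade? |
|---|---|---|---|
| Bilirubin 2 | 2 | 2 | Yes |
| ALT/AST 3 | 1 | 2 | No |
| ALT/AST 5 | 2 | 3 | No |
| ALT/AST 8 | 3 | 3 | Yes |
| ALT/AST 10 | 3 | 3 | Yes |
| ALT/AST 20 | 3 | 4 | No |

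The bilirubin cut-off sits (2.0 − 1.5)/(3.0 − 1.5) = 1/3 of the way into the grade 2 band.

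**Step 2. Elevated baseline** (Protocol 6.3.4.1). With baseline b in multiples of ULN, the effective transaminase limit is min(max(2b, 3), 8).

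- b = 1.2 or 1.5: limit 3, a grade boundary.
- b = 1.6: limit 3.2, inside grade 2. b = 2: limit 4, inside grade 2.
- b = 2.5: limit 5, a grade boundary.
- b = 3: limit 6, inside grade 3. b = 4 or 5: limit 8, inside grade 3.

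Inclusion criterion 7 admits transaminases up to 3 × ULN, or 5 × ULN with liver metastases, so these baselines can occur.

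The bilirubin limit is max(2b, 2). For b = 1.0, 1.2 and 1.4 it is 2.0, 2.4 and 2.8, all inside grade 2. At b = 1.5, the entry limit in criterion 7, it is 3.0, a boundary.

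The SAP's elevated-baseline rows use 3 × baseline or 8 × ULN for transaminases. The twice-baseline limits therefore matter for reconstructing the protocol criterion from the database. The 8 × ULN and bilirubin limits also matter for SAP rows.

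**Step 3. Apply the entry rule to example pairs** (illustrative values, assumed).

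- Bilirubin: central 1.8, local 2.4. Both grade 2; local value not entered.
- ALT: central 2.8, local 3.3. Grades 1 and 2; local value entered.
- ALT: central 7, local 9. Both grade 3; local value not entered.

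**Step 4. Effect on a combined row** (illustrative values, assumed). Central: ALT 3.6, bilirubin 1.9. Local: ALT 4.0, bilirubin 2.4. All four are grade 2, so nothing local is entered.

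- As recorded: ALT 3.6 > 3, bilirubin 1.9 ≤ 2. Combined row not met.
- With the local values: ALT 4.0 > 3, bilirubin 2.4 > 2. Combined row met.

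The gap here is 2.4/1.9 = 1.26, but a large gap is not needed. Central 1.95 and local 2.05 (ratio 2.05/1.95 = 1.05) give the same result.

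**The case against.** The strongest reply has four parts.

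1. **The main transaminase cut-off is safe.** ALT/AST 3 × ULN is exactly the grade 1/2 boundary, so a local crossing that the central result does not share is a grade difference and is entered. This stands. A reader might infer that the transaminase cut-offs in general are lost; the bands do not support that. For elevated baselines up to 1.5 × ULN the limit also stays on the boundary.

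2. **A central sample is meant to exist.** Loss then needs two results of the same grade on opposite sides of a cut-off, which is laboratory disagreement near a threshold, not a missing peak. The follow-up tests in Protocol Table 6-4 (repeats within 48 to 72 hours or weekly monitoring, depending on grade) make it likely that some other value crosses. This stands, and it makes the loss rare. It does not close the gap, because Step 4 is exactly that situation.

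3. **The event is captured elsewhere.** Cases confirmed on repeat testing with no other cause are reported as SAEs (6.3.4.1), laboratory abnormalities requiring a treatment change are AEs (8.1.2.1), and AEs leading to discontinuation are tabulated (SAP 2.8.2). This largely stands. A reader might infer that liver-injury cases would go unrecognised; the documents do not support that. These routes do not ensure that the numeric values reach the laboratory tables or eDISH, and the SAP combined rows are not limited to confirmed or unexplained cases.

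4. **Section 7.2.2.5.2 already asks for unscheduled chemistry results.** It may well govern where no central grade exists for comparison. But a site following the more specific local-laboratory rule would still omit a same-grade value, so the sections need reconciling.

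Two further inferences should be avoided. The Hy's Law case in the Amendment 2 rationale came from another study, of INC280 with gefitinib, and shows nothing about this entry rule. And the SAP says how to pool the local values it has; it does not state that local capture is complete.

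**Conclusion.** The concern holds in limited form. Entry by grade difference does not match the bilirubin 2 × ULN cut-off, the elevated-baseline transaminase limits (8 × ULN and most twice-baseline values), or the SAP rows above 8 and 10 × ULN. It does match the 3 × ULN transaminase cut-off.

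A patient is lost from a liver table only if three things coincide: the paired results share a grade, the local value alone is above the cut-off, and no other recorded value crosses it. The documents give no data on central-to-local disagreement or on how often local tests are done, so the count cannot be estimated; it is probably small. No efficacy result and no treatment decision at the site depends on it. What is affected is the completeness of the liver-safety tables, always towards fewer recorded elevations, together with a plain inconsistency between 7.2.2.5 and 7.2.2.5.2.

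This assumes that the severity grade in 7.2.2.5 means the bands printed in Table 6-3, and that sites follow the specific rule in 7.2.2.5 over the general one.

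**What to change.** Reconcile Protocol 7.2.2.5 with 7.2.2.5.2 by adding to 7.2.2.5:

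- Local ALT, AST, total bilirubin and ALP results obtained for an urgent safety decision are entered, with the local ULN, whether or not their grade agrees with the central result.
- Local results for these four analytes are also entered whenever no central result is available.
- The grade-difference rule stays for all other parameters.

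The SAP needs no change, since it already pools both sources and takes the worst value.

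The cost is slightly more data entry and normal-range collection for four analytes, on a local laboratory eCRF page that already exists. No test is added and no clinical rule changes.
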